7.3 Safety and Health Economic Outcomes Analysis

The ITT population will be used for all safety and health economic analyses. Statistical summaries will be produced in accordance with section 7, and listings will be generated by site, subject, and visit within subject. For the purposes of this analysis, coding dictionaries will not be utilized.

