 Pregnancy test, if applicable, completed within 7 days of Index Procedure. May be completed on day of Index Procedure.

 For the purposes of determining IMA, HVA and MAA for patient eligibility, measurements will be made according to institutional SOC. For the purposes of all data analysis, measurements made by the Central Radiologist will be utilized. If there are minor differences in baseline IMA, HVA and MMA measurements made by the central radiologist, the measurements of the PI/site will remain acceptable for determining patient eligibility.

 Confirm exclusion criterion “patient is not a current nicotine user” prior to start of anesthesia. If subject indicates current use of nicotine, patient should be considered a screen failure.

 If subject requires an incision >4.0 cm to complete the Lapiplasty® Procedure, the subject should be considered a screen failure.

 Documentation for return to weight bearing activities include time to start weight-bearing in boot, time to start weight-bearing in shoe, and time to full unrestricted activity.

 ROM - dorsiflexion and plantarflexion should be measured while subject is passive and non-weightbearing with the study provided goniometer.

 Secondary surgical interventions, Wound healing requiring intervention, infection requiring intervention, hardware removal, revision procedure of 1st ray, other complication requiring surgical intervention.

 Only AEs related to the Lapiplasty® Index Procedure or the Lapiplasty® System Implants will be recorded on the eCRF.

 Radiographic Measurements are completed by the Central Radiologist only.

 Health Economic Outcomes, see Secondary Endpoints for data to be recorded on eCRF.

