#### **8.1.8 Medical Dictionary Coding**

Medical dictionary coding will be performed using a coding thesaurus algorithm. The MedDRA will be used upon data entry and query resolution for AEs and SAEs, via automated and manual coding processes.

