### **10.2.3 Adverse Event Classification**

The investigator is required to provide:

- Time interval of the event – The time interval of the occurrence of the adverse event should be assessed in relationship to timing of the index procedure (Lapiplasty® Procedure)
- Date of event onset and outcome of the event, or date of death

- Severity of the event – (Mild, Moderate, Severe)
- Action taken for medical management of the event
- Relationship of the event – it is the PI's responsibility to assess the relationship of an AE and provide primary cause. Events will be categorized by relationship to the Lapiplasty® System Implants, the Lapiplasty® System Reusable Instruments, or the index procedure (Lapiplasty® Procedure).
- Adverse events will be assessed to determine if the event meets the definition of a serious adverse event.

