#### 10.2.4 Reporting Adverse and Serious Adverse Events

The investigator (or designee) will record all AEs (both serious and non-serious and regardless of relationship) in the source documents. The Investigator at each participating site is responsible for reporting AEs and SAEs to TMC only when they are related to the Lapiplasty® Procedure, the Lapiplasty® Mini-Incision™ System Implants and Lapiplasty® Mini-Incision™ Precision Instrument Set. AEs related to the Lapiplasty® Procedure or Lapiplasty® devices will be reported on the eCRF. The CRF allows the investigator to indicate whether an adverse event is related to the Lapiplasty® System devices or Lapiplasty® Procedure (index procedure).

- Use a separate Adverse Event Form to document each event
- The Adverse Event Form must be electronically signed by the Investigator

*Note: It is the responsibility of the Investigator to inform their IRB of SAEs as required by their IRB procedures and in conformance with FDA requirements.*

For the purposes of this study, the following adverse events are not considered reportable (recorded on eCRF) because they are normally expected to occur in conjunction with surgical treatment for hallux valgus procedures or are associated with customary and standard care of patients undergoing surgical treatment of hallux valgus or other protocol approved and acceptable concomitant procedures. If any of these events are **beyond what is normally expected** after the Lapiplasty® Procedure, they should be reported as AEs. However, the decision to report any AEs is ultimately the decision and responsibility of PI.

- Post-operative pain/post-procedure pain
- Minor, localized tenderness, swelling, induration, oozing, etc. at surgical site
- Temporary numbness or tingling at surgical site
- Elevated White Blood Cell count without signs and symptoms of infection
- Stiffness/weakness of joint

*Note: Subjects will undergo general anesthesia and therefore will also be subject to general anesthesia-associated complications and morbidity. These are also not considered reportable (recorded on eCRF) adverse events.*

Any pre-planned surgical procedures

- Any pre-planned surgical foot procedures at the time of informed consent will not be considered reportable (recorded on eCRF) adverse events (whether hospitalization is required or not).

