1.2.2 Secondary Endpoints

- 1) Change from baseline in radiographic angular/positional alignment at 6 weeks, 4 months, 6 months, 12 months, and 24 months post-Lapiplasty® Procedure.
- 2) Percentage of subjects with absence of clinical/radiographic healing, or non-union, at 12 months post-Lapiplasty® Procedure.
- 3) Clinical complications through 24-month follow-up visit due to the Lapiplasty® System Implants, the Lapiplasty® Procedure, the post-operative weight-bearing protocol or health conditions that could affect other outcome measures.
- 4) Time to start weight-bearing in boot, in days.
- 5) Time to start weight-bearing in shoes, in days.
- 6) Time to return to full unrestricted activity, in days.
- 7) Change from baseline in pain at the base of the big toe (bunion related) assessed via a Visual Analog Scale (VAS) at 0-14 days, 14-21 days, 6 weeks, 4 months, 6 months, 12 months, and 24 months.
- 8) Change from baseline in Quality of Life at 6 months, 12 months, and 24 months as measured by PROMIS-29 (for adult subjects), PROMIS-25 (for pediatric subjects), and MOxFAQ (for all subjects).
- 9) Change from baseline in range of motion (ROM) of 1st MTP dorsiflexion and plantarflexion at 12 months and 24 months.
- 10) Change, if any, in incision length during the Lapiplasty® Procedure.
- 11) Change from baseline in radiographic foot length and width at 12 months post-Lapiplasty® Procedure.
- 12) Change in swelling at 6 weeks and 4 months post-Lapiplasty® Procedure as compared to 0-14 day visit.
- 13) Change in scar quality at 4 months, 6 months, and 12 months post-Lapiplasty® Procedure.
- 14) Correlation between amount of time external positioner is actively used during Lapiplasty® Procedure with necrosis, blistering, bruising, and tissue ulceration events.

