7.3.1 Adverse Events

Adverse events (AEs) related to the Lapiplasty® Procedure and the Lapiplasty® devices that are captured at the time of the index procedure and up until the time of the last study visit will be included in the analysis. Number and proportion of subjects with at least one AE, total number of AEs, and number of subjects with at least one AE by AE type will be summarized using the reported AE term, and the following summaries will be generated:

- All AEs
- Serious AEs (SAEs)
- AEs leading to death
- AEs leading to device removal/surgical intervention
- AEs leading to study discontinuation

Subject level listings will also be produced and will include subject ID, age, sex, AE term, AE description, AE start and end dates, action taken, outcome, primary relationship, secondary relationship, and SAE (y/n).

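### Two of the four causes named in secondary endpoint 3 have no systematic adverse-event capture; separately, the SAP sets aside the protocol's MedDRA coding without a rationale

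*SAP*

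**What the plan says.** **Endpoint.** Secondary endpoint 3 (protocol 3.0, SAP 1.2.2) covers complications through 24 months due to the implants, the procedure, "the post-operative weight-bearing protocol or health conditions that could affect other outcome measures". The two documents agree on these four causes.

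**Capture.** Footnote 14 to the protocol's Schedule of Assessments, repeated in SAP 1.5, states: "Only AEs related to the Lapiplasty® Index Procedure or the Lapiplasty® System Implants will be recorded on the eCRF". Protocol 10.2.4 adds that the investigator "is responsible for reporting AEs and SAEs to TMC only when they are related to the Lapiplasty® Procedure" or to the implants or instrument set; all other events stay in source documents. Protocol 9.7 and SAP 7.3.1 apply the same restriction to the safety analysis. On cause, protocol 10.2.3 states: "Events will be categorized by relationship to the Lapiplasty® System Implants, the Lapiplasty® System Reusable Instruments, or the index procedure".

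**Coding.** Protocol 8.1.8 states: "The MedDRA will be used upon data entry and query resolution for AEs and SAEs, via automated and manual coding processes". SAP 7.3 states: "For the purposes of this analysis, coding dictionaries will not be utilized". Under SAP 7.3.1 the "number of subjects with at least one AE by AE type will be summarized using the reported AE term". Protocol 9.8 asks the SAP to give reasons for changes to the analysis; the SAP gives none for this one.

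**The concern.** These are two separate points, and the first is the weightier.

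On capture, the endpoint is wider than the data meant to feed it. Early weight-bearing is in the study title, and Objective 3 asks about its effects. A complication that an investigator puts down to weight-bearing alone, or to a health condition, falls inside endpoint 3 but outside the rule for completing an adverse-event form. Endpoint 3 would then be under-counted for those causes, and a reader of the report could take the absence of such events as a finding.

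On coding, up to 20 sites will report events. If sites word the same event differently and nothing groups the terms, a by-type table shows several small rows where there should be one. Grouping them later, in an unblinded study with the events already known, would be a post hoc choice.

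**Working it through.** The documents give no figure to reproduce on either point: the sample size of 200 has no formal calculation, and safety is descriptive. The check sets the provisions side by side; the arithmetic only illustrates size.

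**1. Capture, cause by cause**

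| Cause in endpoint 3 | Goes on the AE form (footnote 14, 9.7, 10.2.4)? | Relationship category (10.2.3)? | In the SAP 7.3.1 analysis? |
|---|---|---|---|
| Implants | Yes | Yes | Yes |
| Procedure | Yes | Yes | Yes |
| Weight-bearing regimen | Not if this is the sole cause | None listed | No |
| Health condition | Not if this is the sole cause | None listed | No |

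Is endpoint 3 analysed anywhere else? It is not in the SAP 7.2.2 list. SAP 7.3.2 counts complications that led to an intervention and does not break them down by cause. Table 25 is given by title only. The SAP 7.3.1 listing has a primary and a secondary relationship field, but no document gives either field a value for the two uncovered causes.

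Other routes into the database:

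- Secondary surgical interventions (protocol 7.12): any complication needing further surgery, but only those.
- Delayed weight-bearing (5.3): the reason is recorded, but as a protocol deviation.
- Central radiographic review (Appendix 4): hardware problems and possible complications visible on film.
- Investigator discretion (10.2.4): an investigator may attribute a weight-bearing event to the procedure and report it. Section 5.1, however, confines the index procedure to use of the system at operation, and an event reported this way loses its cause.

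None of these yields complications by cause.

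*Illustration (assumed rates).* Let 20 of 200 subjects have an endpoint 3 complication, let a share s arise solely from the two uncovered causes, and let none of those arrive by another route. Recorded subjects = 20 × (1 − s). Intervals are exact (Clopper-Pearson) 95%.

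| s | Recorded | Rate | 95% CI |
|---|---|---|---|
| 0 | 20 | 10.0% | 6.2% to 15.0% |
| 0.10 | 18 | 9.0% | not needed here |
| 0.25 | 15 | 7.5% | 4.3% to 12.1% |
| 0.50 | 10 | 5.0% | 2.4% to 9.0% |

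**2. Coding**

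The protocol rule governs data management and the SAP rule governs analysis. Both can be obeyed at once only if the codes are stored and then ignored. The SAP names no other way of grouping terms.

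*Illustration (assumed split).* Let one kind of event affect 10 of 200 subjects, one report each, spread evenly over k wordings. Rate per row = (10/k)/200.

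- k = 1, which includes a pick-list: 10/200 = 5.0%
- k = 2: 5/200 = 2.5%
- k = 5: 2/200 = 1.0%

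The number of subjects with any adverse event stays at 10 for every k. Counts of serious events and the intervention-based counts in SAP 7.3.2 do not depend on the wording either.

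**The case against.** The strongest reply is that each mismatch does less harm than it seems to.

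On capture, Objective 3 concerns union and loss of correction. Those come from central radiographs and the joint-pain assessment, whatever cause an investigator assigns to an adverse event. Weight-bearing dates and late starts are recorded, and complications needing surgery are captured. This stands. A reader might infer that weight-bearing complications cannot reach the database at all, or that the study says nothing about the regimen. The documents support neither reading, because of these outcomes and the partial routes listed above. What remains is narrower: events with one of the two uncovered causes alone that did not need surgery.

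On coding, the protocol leaves analysis detail to the SAP, and the SAP limits its statement to this analysis. The phrase "will be summarized using the reported AE term" does not say that the term is free text; the listing has separate fields for AE term and AE description, which would also fit a pick-list. The form is not among the documents. All reported events are listed by subject, so a reader could regroup a small set. This too stands in part: fragmentation is a possibility, not a fact. It does not supply the missing rationale or a grouping rule.

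A reader might also join the two points and infer that the lack of coding prevents endpoint 3 from being delivered. It does not. Coding affects only the by-type rows; the capture rule is what limits the endpoint.

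**Conclusion.** Both points hold in this limited form, and the plan should be changed.

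1. **Capture.** As written, endpoint 3 cannot be reported by its four causes. The size of the under-count is unknown. It depends on the complication rate, on the share due solely to the uncovered causes and on how often investigators attribute such events to the procedure. Under the assumptions above, the recorded rate falls from 10.0% to between 9.0% and 5.0%.
2. **Coding.** The SAP departs from the protocol without explanation. The effect on by-type incidence runs from none, with a pick-list, to a division by the number of wordings. No particular multiple can be claimed from the documents.

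Confidence is high that the provisions disagree, and lower that by-type rows would in fact fragment, since that rests on an unseen form.

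**What to change.** **Capture: choose one and state it.**

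- *Widen capture.* Add the post-operative weight-bearing protocol and a health condition affecting study outcomes as relationship categories in protocol 10.2.3. Amend footnote 14 in both documents, protocol 9.7 and 10.2.4, and the relatedness restriction in SAP 7.3.1, so that these events are both recorded and analysed. Without the SAP 7.3.1 change, newly recorded events would still fall outside the tables. Add a table of endpoint 3 by cause, not limited to complications needing intervention. Cost: a protocol amendment with IRB review, an eCRF change and some extra adverse-event forms. Do this first, because events left only in source notes may be hard to recover consistently.
- *Narrow the endpoint.* Restrict endpoint 3 in both documents to procedure- and device-related complications and say so in the report. Cost: an amendment to the text, with no new data collection.

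**Coding: choose one.**

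- Delete the SAP 7.3 sentence and tabulate adverse events by MedDRA system organ class and preferred term, keeping reported terms in the listings. Cost: small, since the protocol already plans the coding.
- Keep reported terms, amend protocol 8.1.8, give the rationale that 9.8 asks for, and fix a term-grouping list before analysis. Cost: a protocol amendment and the work of drawing up the list.

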7.3.1 Adverse Events

Adverse events (AEs) related to the Lapiplasty® Procedure and the Lapiplasty® devices that are captured at the time of the index procedure and up until the time of the last study visit will be included in the analysis. Number and proportion of subjects with at least one AE, total number of AEs, and number of subjects with at least one AE by AE type will be summarized using the reported AE term, and the following summaries will be generated:

- All AEs
- Serious AEs (SAEs)
- AEs leading to death
- AEs leading to device removal/surgical intervention
- AEs leading to study discontinuation

Subject level listings will also be produced and will include subject ID, age, sex, AE term, AE description, AE start and end dates, action taken, outcome, primary relationship, secondary relationship, and SAE (y/n).

7.3.2 Clinical and Hardware Complications

The health economic outcomes analysis will determine the following endpoints:

Percentage of subjects experiencing clinical complications through 24 months requiring one or more subsequent interventions: a deviation or delay from the normal operative plan, readmission to hospital, return to operating room, unscheduled visits due to complications (revisions, hardware removals, reoperations, supplemental fixations, wound healing requiring surgical intervention, infection at surgical site requiring surgical intervention), employment of home health services, time (in days) to return to work and to full work, and percentage of subjects requiring post-operative physical therapy.

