## **9.6 Interim Analyses**

Interim analyses will be performed during the study according to patient enrollment and availability of data of interest. Interim analyses will be used to provide early information about the safety and efficacy of the procedure and may be used for internal decision making, hypothesis generation, abstraction/publication for major orthopedic conferences, or other purposes, as applicable. Interim analyses will follow the methods in the statistical analysis plan.

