6.2 Analysis Populations

6.2.1 Intent-to-Treat Population

The Intent-to-Treat (ITT) population is defined as all enrolled subjects who met inclusion/exclusion criteria and were treated with the Lapiplasty® Procedure using the Mini-Incision System.

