6.3 Missing Data

Effectiveness and health economic analyses will be based on available data, without imputation for missing values. For Quality of Life outcomes (MOxFQ and PROMIS-29/PROMIS-25), missing data will be handled as specified in the Derived Variables section. For safety analyses, missing event dates will be imputed as follows:

- If only month and year are reported, then day is assigned as the 15th of the month
- If only year is reported, then month and day is assigned as July 1st

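### AE and complication percentages have no stated denominator or rule for unequal follow-up: a modest understatement at the final analysis, potentially a large one at interim analyses that may be published

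*SAP*

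**What the plan says.** - **Population.** SAP 7.3: "The ITT population will be used for all safety and health economic analyses". SAP 6.2.1 defines ITT as "all enrolled subjects who met inclusion/exclusion criteria and were treated with the Lapiplasty® Procedure using the Mini-Incision System". There is no follow-up requirement.
- **AEs.** SAP 7.3.1 reports "Number and proportion of subjects with at least one AE, total number of AEs". It counts events "captured at the time of the index procedure and up until the time of the last study visit", so the window differs by subject. No 24-month label is attached.
- **Complications.** SAP 7.3.2 reports the "Percentage of subjects experiencing clinical complications through 24 months requiring one or more subsequent interventions". This is the only safety percentage with a 24-month label.
- **Missing data.** SAP 6.3 says "Effectiveness and health economic analyses will be based on available data, without imputation for missing values", and SAP 7.3.2 describes itself as a health economic analysis. For safety, the rule begins "For safety analyses, missing event dates will be imputed as follows" and deals only with partial dates. It does not address incomplete follow-up.
- **Tables.** SAP 7 has each table show the total relevant population, with missing observations included. The AE tables are titled for the ITT population.
- **Interim analyses.** Protocol 9.6 times them by enrollment and data availability, lists conference abstracts and publication among possible uses, and states "Interim analyses will follow the methods in the statistical analysis plan". The body of the SAP has no interim section and no data-cut rule.

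No time-to-event estimate, person-time rate, censoring rule or number at risk is given for AEs or complications.

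**The concern.** Events can be seen only while a subject is under observation. Protocol 4.2.5 foresees withdrawal, loss to follow-up and site termination, and at any interim the later-treated subjects have short follow-up. If such subjects stay in the denominator with no recorded event, they are treated as event-free for time nobody observed, and the percentage falls below the cumulative risk it appears to describe.

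The study has no comparator arm, so the absolute rates are the safety result, and complications through 24 months are a listed secondary endpoint. An error in this direction favours the device, and it would be largest in results that could be published first.

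**Working it through.** **No design figure to reproduce.** The documents give N = 200 and up to 2 years of follow-up. They give no dropout, accrual duration, event rate or event timing. Everything below that depends on those is assumed.

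**Model 1: share of 24-month events captured if all treated subjects form the denominator.** Share = average over event times t of S(t) × G(t). S is the probability of not having dropped out by t, taken as exponential and independent of events. G is the probability that follow-up available at the data cut reaches t. There are three event-time patterns:
- early: 60% in months 0-3, 40% spread evenly over months 3-24;
- uniform over 0-24;
- late: uniform over 4-24, as might suit hardware removal.

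*Final analysis (G = 1).* For uniform events the share is d / (−ln(1−d)), where d is the 24-month loss. At 10%, 0.10/0.1054 = 94.9%. At 20%, 0.20/0.2231 = 89.6%.

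| Loss | Early | Uniform | Late |
|---|---|---|---|
| 10% | 97% | 95% | 94% |
| 20% | 95% | 90% | 88% |

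*Interim, 18 months of uniform accrual, no dropout.* A cut at the end of accrual makes follow-up uniform over 0-18 months:
- early: [0.9 + 9 + (0.4/21) × 112.5]/18 = 12.04/18 = 67%;
- uniform: 9/24 = 37.5%;
- late: (98/20)/18 = 27%.

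A cut six months later makes follow-up uniform over 6-24 months, mean 15:
- early: 0.6 + 0.4 × 12/21 = 83%;
- uniform: 15/24 = 62.5%;
- late: 11/20 = 55%.

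*Interim with 10% and 20% loss, by numerical integration:*

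| Cut | Early | Uniform | Late |
|---|---|---|---|
| End of accrual | 66%, 65% | 37%, 35% | 26%, 25% |
| Six months later | 81%, 80% | 60%, 58% | 52%, 50% |

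**Model 2: different assumptions.** Exits are uniform over 0-24 months and the true 24-month risk is 10%. Crude = (1−d) × 10% + d × (mean risk accrued by exit).
- Constant hazard: mean accrued risk = 1 − 0.10/0.1054 = 5.09%. Crude is 0.9 × 10 + 0.1 × 5.09 = 9.5% at 10% exit, and 0.8 × 10 + 0.2 × 5.09 = 9.0% at 20%.
- Front-loaded (70% of risk by month 4): mean accrued risk = 10% × (4 × 0.35 + 20 × 0.85)/24 = 7.67%. Crude is 9.8% and 9.5%.

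Simulated with N = 200, one minus Kaplan-Meier returned 9.9-10.0% in all four cases. With interim follow-up spread over 0-24 months and 10% exit, crude was 4.9% (constant) or 7.6% (front-loaded), against 9.9% by Kaplan-Meier.

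Across both models the final-analysis understatement is about 2-6% relative at 10% loss and 5-12% at 20%.

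**The alternative denominator.** If SAP 6.3 is read as restricting 7.3.2 to subjects with 24-month data, the answer can move further. Take 200 subjects, 20 with an event, and suppose those same 20 are the ones who exit. All-ITT gives 20/200 = 10%, which is exact. Completers-only gives 0/180 = 0%.

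**Side check.** The background nonunion figure of 1.6% matches 1/61 (feet reaching the 1-year endpoint), not 1/72 = 1.4%. The documents' own reference rate therefore appears to use a followed-up denominator.

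**The case against.** A reader might infer that the plan divides every AE and complication percentage by all ITT subjects, and that the reported 24-month safety rates will therefore be understated. The documents do not support that strength of claim.

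- **The denominator is not written.** SAP 7.3 names a population, and SAP 6.3 could be read as excluding subjects without data from 7.3.2. This stands: all-ITT is the natural reading, not a stated rule. It does not clear the plan, because two denominators remain open for one percentage and completers-only would discard events in subjects who exited early.
- **AEs carry no 24-month label.** This stands.
- **The final effect is small.** At a true 10% with 10% loss, the gap is 0.2-0.5 points against a 95% half-width of 1.96 × √(0.1 × 0.9/200) = 4.2 points. In a descriptive single-arm study, crude n (%) is a common choice. This stands for the final report.
- **Exits may follow events.** Protocol 4.2.5 lists adverse events and device or procedure failure as exit reasons. Such subjects already carry an event, so for any-AE the bias shrinks or vanishes. This stands, although later distinct events would still go unseen.
- **The late pattern does not fit the composite.** SAP 7.3.2 includes deviations from the operative plan, which arise at surgery. This stands: the lowest figures apply to outcomes such as hardware removal.
- **Interim publication is permitted, not promised.** Protocol 9.6 does not say that unfollowed subjects will be counted. This stands, but nothing in either document prevents it.
- **Kaplan-Meier has limits.** It assumes non-informative censoring, and no 24-month estimate exists where nobody has reached 24 months. Both limits stand and shape the fix.

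**Conclusion.** The concern holds in a limited form. The SAP specifies crude proportions on a population with no follow-up requirement, leaves the denominator open, and has no method for unequal follow-up. Protocol 9.6 extends this to interim analyses that may be published.

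At the final analysis the likely understatement is modest: about 2-6% relative at 10% loss and 5-12% at 20%, less where exits follow events. This does not show that the final safety result would be materially biased. At an interim it can be large: with 18 months of uniform accrual and 10-20% loss, a cut at end of accrual captures roughly 25-66% of 24-month events, and a cut six months later roughly 50-81%.

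These sizes rest on an all-ITT denominator, dropout independent of events, and assumed accrual and event timing. The direction would not be assured under a different denominator or with event-driven exits.

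**What to change.** In SAP 7.3.1 and 7.3.2:
1. State the denominator of each percentage. For 7.3.2, say how SAP 6.3 applies, and do not restrict to subjects with 24-month data.
2. For any AE, SAE, and AEs leading to device removal or surgical intervention, add Kaplan-Meier cumulative incidence with 95% CI and number at risk at 6, 12 and 24 months. Use AE onset date and censor at last visit or study exit.
3. Keep crude n (%) beside a summary of follow-up time.
4. For interim analyses, state the data cut, report only those timepoints that enough subjects have reached, and do not label a crude interim percentage as running through 24 months.

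The cost is SAP wording and a few more summaries. AE onset dates (Protocol 10.2.3) and exit dates (Protocol 7.11) are already collected, and SAP 6.4.1 already derives time to follow-up. Protocol 7.12 names no date for secondary surgical interventions, so those estimates would be timed by onset of the AE, not by the operation. Reported rates would be slightly higher. Kaplan-Meier assumes non-informative censoring, so reasons for exit should be shown alongside.
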